**8.1.3 Safety Analysis/Secondary Aim**

The outcome will be measured at 30 and 180 days for all 6 subgroups: all coded as 0 or 1 at both follow-up points.

The analysis plan for this aim is very similar to that for the Primary Aim except the outcome here is defined as intracranial hemorrhage (which is coded as a 0 and 1 variable), and (2) the hypotheses for the outcomes are directional and therefore one-sided tests will be performed. AE incidence will be summarized along with the corresponding 95% confidence intervals.

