### **3 STUDY OBJECTIVES**

#### **3.1 Research Hypothesis**

Early anticoagulation treatment regimen with Apixaban at 0-3 days after TIA, 3-5 days after small ischemic stroke and 7 to 9days after medium ischemic stroke for patients with atrial fibrillation will result in a decreased incidence for recurrent ischemic stroke and without significant increase in risk of intracranial hemorrhage compared to conventional treatment for TIA, small and medium sized strokes.

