#### **3.3 Secondary Objectives**

In patients with atrial fibrillation with recent cerebral ischemic symptoms (0-48 hours), to evaluate whether the treatment regimen of early Apixaban (Three subgroups: TIA: day 0-3; small stroke: day 3-5; medium stroke: day 7-9) compared with standard of care treatment with warfarin (three subgroups: TIA: day 7±5; Small or medium stroke: day 14±5) does not increase the number of intracranial hemorrhage assessed by MRI/CT by 30 and 180 days.

Additional information will be collected on:

- Quality of Life
- Modified Rankin Score
- NIH Stroke Scale
- Echocardiography
- AF Burden (Event Monitor data).

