## 7.2 Secondary Endpoints

- Any intracranial bleeds assessed by MRI/CT scan at day 14 and EOS or at outcome event.
- Any major bleeds defined as clinically overt bleeding that was accompanied by one or more of the following: a decrease in hemoglobin of 2 g/dL or more; a transfusion of 2 or more units of packed red blood cells; bleeding that occurred in at least one of the following critical sites: intracranial, intraspinal, intraocular, pericardial, intra-articular, intramuscular with compartment syndrome, retroperitoneal; or bleeding that was fatal. Intracranial hemorrhage included intracerebral (hemorrhagic stroke), subarachnoid, and subdural bleeds.

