#### **8.1.2 Efficacy Analysis/Primary Aim**

For the main outcomes, the proportion of patients with any primary outcome (fatal stroke, recurrent ischemic stroke, transient ischemic attack) will be computed along with the 95% confidence interval for the differences in treatment arms.

The primary outcome is defined as any component of the composite primary outcome occurred within 30 and 180 days or otherwise had adequate follow-up. Logistic regression models will be fitted with the primary outcome as the dependent variable and the SUBGROUP: (1) Apixaban TIA: day 0-3; (2). Apixaban small stroke: day 3-5; (3). Apixaban medium stroke: day 7-9; (4) warfarin TIA: day 7±5; (5) warfarin small stroke: day 14±5; (6) warfarin medium stroke: day 14±5 as the primary independent variable. The overall treatment effect will be assessed by the ESTIMATE and LSMEANS of all the Apixaban groups to all the warfarin groups. Comparison between individual subgroups will be assessed by constructing different ESTIMATE. For example, (1) Apixaban TIA versus (5) warfarin Small stroke: day 14±5. These analyses will be implemented by using SAS 9.2 PROC LOGISTIC which has the ESTIMATE and the LSMEANS statements for the group comparisons. P<0.05 is used for the overall treatment effects. All other subsequent subgroup testing will be adjusted for multiple comparisons by using PROC PLM.

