**8.1.5 Sample Size and Power**

As a pilot, open-label study, this project is intended to generate data to be used in the development of future, larger studies. A total of 120 patients are expected to be available and eligible to participate in this study and up to 125 may be screened in order to yield 120 randomized participants.

Review of our database indicates the risk of fatal or recurrent stroke in patients with atrial fibrillation is approximately 20% with standard treatment . To calculate expected power in this study, this established risk was used as the basis for estimates that could be expected with this treatment if it is successful. Given the parameters of conducting a 2-sided test with alpha = .05, and equal allocation to treatment and control groups (50 patients per group), power calculations were conducted using various ratios of outcomes (i.e. fatal or recurrent stroke) in the control group compared to the experimental group. The following results were obtained:

Power	Detectable outcome Risk in control / Risk in experimental
80% power	2.30

90% power	2.52
99% power	3.00

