### 8.1.6 Randomization

Randomization of treatment was calculated in SAS 9.4 using a stratified, blocked PLAN procedure. For the 120 subjects to be randomized to either apixaban or warfarin, a random seed number was generated. Each subgroup of stroke type (small stroke, medium stroke and TIA) was randomized implementing block randomization using four blocks of 10. The treatment allocation was created by an unblinded statistician and given to the TGH research pharmacy. Blinded study envelopes are provided to study team members for randomization.

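### The no-increase aim for intracranial haemorrhage rests on a one-sided zero-null contrast with no rule for reading the interval, so a non-significant result cannot support it

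*Combined protocol and SAP*

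**What the plan says.** Section 3.3 sets the secondary objective: to evaluate whether early apixaban, compared with standard-timed warfarin, "does not increase the number of intracranial hemorrhage assessed by MRI/CT by 30 and 180 days". The research hypothesis in 3.1 puts the same idea as "without significant increase in risk of intracranial hemorrhage compared to conventional treatment".

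The analysis is in 8.1.3: "The analysis plan for this aim is very similar to that for the Primary Aim", apart from two changes. The outcome becomes ICH, coded 0 or 1, and "the hypotheses for the outcomes are directional and therefore one-sided tests will be performed". The plan carried over from 8.1.2 is a logistic model on a six-level factor (two arms by TIA, small stroke and medium stroke), in which "The overall treatment effect will be assessed by the ESTIMATE and LSMEANS of all the Apixaban groups to all the warfarin groups".

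Section 8.1.2 also supplies a 0.05 threshold for overall treatment effects and a 95% confidence interval for the difference between arms. Section 8.1.3 itself adds only 95% intervals for adverse event incidence. Neither section writes out a null hypothesis, a direction, a one-sided level, a margin or a rule for the upper limit of the ICH difference. The power statement in 8.1.5 covers only fatal or recurrent stroke.

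**The concern.** An aim of no increase is supported by an interval that excludes increases of a size that matters. It is not supported by failing to reject a null of zero difference, because a small trial fails to reject for many true effects, including harmful ones.

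Sections 3.1 and 3.3 make a test for an increase the natural reading of 8.1.3. On that reading, and with the word significant in 3.1 taken statistically, a null result meets the hypothesis, and the smaller the trial the easier that is.

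ICH is the main safety question raised by starting anticoagulation earlier. Section 8.1.5 says that "this project is intended to generate data to be used in the development of future, larger studies", so a statement of no significant increase would be carried into the design of those studies.

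A second weakness comes with the contrast borrowed from 8.1.2. With few events spread over six cells, it will often have no finite estimate.

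**Working it through.** The plan gives no power, sample size or margin for ICH, so there is no figure of its own to reproduce. The check asks how informative a non-significant result would be.

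**Inputs from the documents.** 120 patients, 1:1, so 60 per arm (4.1, 8.1.5). Section 8.1.6: "Each subgroup of stroke type (small stroke, medium stroke and TIA) was randomized implementing block randomization using four blocks of 10", so 40 per stratum and about 40/2 = 20 per arm-by-stratum cell.

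**Assumptions.** No ICH rate for this population is given; Table 3 has only annual rates from the pivotal trials. Section 7.2 counts "Any intracranial bleeds assessed by MRI/CT scan at day 14 and EOS or at outcome event", so imaging-detected bleeds are included and a risk above 10% cannot be ruled out. The control risk is therefore varied over 2, 5, 10, 15 and 20%. The true apixaban risk is set at twice the control risk.

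**Step 1: chance of missing a doubling with a simple two-arm test.** All outcomes of Binomial(60, p) against Binomial(60, 2p) are enumerated. The score statistic is z = (x1 − x0)/60 ÷ √[p̄(1 − p̄)(2/60)], with p̄ = (x1 + x0)/120. Because 8.1.3 does not fix the level, both candidates are shown.

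| Control risk | Score, 0.05 | Fisher, 0.05 | Score, 0.025 | Fisher, 0.025 |
|---|---|---|---|---|
| 2% | 84% | 97% | 93% | 99% |
| 5% | 71% | 83% | 83% | 91% |
| 10% | 54% | 63% | 67% | 75% |
| 15% | 36% | 45% | 49% | 58% |
| 20% | 22% | 29% | 32% | 40% |

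Up to a control risk of 10%, a real doubling is missed more often than found, whichever test and level apply.

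**Step 2: the contrast actually planned.** It is the mean of three apixaban logits minus the mean of three warfarin logits, with Wald SE = √{Σ over six cells [1/x + 1/(20 − x)]}/3. A cell with no event has an infinite logit, so the contrast is not finite. Any arm with fewer than three haemorrhages must leave at least one of its three cells empty. With equal risks p, P(at least one empty cell) = 1 − [1 − (1 − p)^20]^6. At 5%: 0.95^20 = 0.358, 1 − 0.358 = 0.642, 0.642^6 = 0.070, giving 0.93.

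| Control risk | Any empty cell, equal risks | Finite, doubled risk | Finite and significant at one-sided 0.05, doubled risk |
|---|---|---|---|
| 2% | 99.9% | 0.6% | <0.1% |
| 5% | 93% | 18% | 1% |
| 10% | 54% | 65% | 21% |
| 15% | 21% | 89% | 53% |
| 20% | 7% | 97% | 75% |

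**Step 3: what a non-significant result leaves open.** Suppose 4 haemorrhages on apixaban and 1 on warfarin. Then p̄ = 5/120 = 0.0417, SE = √(0.0417 × 0.9583 × 2/60) = 0.0365, z = 0.05/0.0365 = 1.37, and one-sided p = 0.085 (Fisher 0.18). The 95% interval for the difference is −3.2 to +14.7 points (stratified Miettinen-Nurminen, cells 2, 1, 1 against 1, 0, 0). With no haemorrhage in either arm the stratified upper limit is still +6.2 points.

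**The case against.** The strongest reply is that much of what is needed is already in the plan. The cross-reference that brings the six-cell contrast into 8.1.3 also brings the 0.05 threshold and, arguably, the 95% interval for the arm difference. The trial is a pilot and need not set a non-inferiority margin. This stands. A reader might infer that the safety aim has no significance level and no interval; 8.1.2 does not support that. What is missing is narrower: one-sided 0.05 or 0.025, the direction, and how the interval is to be read for ICH.

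A second reply is that the direction is inferred, and that significant in 3.1 could be meant clinically. This also stands. Section 8.1.3 says only that the hypotheses are directional, and the background stresses fewer intracranial bleeds with the newer agents, so a test for a reduction is conceivable. A reader might also infer that the plan commits the sponsor to reporting non-significance as proof of safety. No section says so, and the wording of 3.3 is not itself met by a null result. The point is therefore conditional on the natural reading of 3.1 and 3.3.

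A third reply is that the rates are assumed, that 20 per cell is approximate, and that the empty-cell problem belongs equally to the primary aim. All true. The range is wide, but non-significance is weak evidence over most of it, and 8.1.3 inherits the problem for an outcome that may well be sparse.

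Finally, a reader might infer that patients are left unprotected. They are not. DSMB review (2.2) and the suspension criteria (7.5.2) do not depend on this test. Nor do they answer 3.3: the trial-wide criterion counts symptomatic events in the apixaban arm only.

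**Conclusion.** The point holds in a conditional form. Sections 3.1 and 3.3 pose a no-increase question. Section 8.1.3 answers it with a one-sided contrast against zero difference, without stating direction, exact one-sided level, margin or how the interval is to be read. If the test looks for an increase and significance is statistical, a null result meets 3.1 without showing that a material increase is absent.

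The size depends on assumed control risks of 2 to 20%, 60 per arm and a true doubling. At one-sided 0.05 the miss rate runs from 84% down to 22% with the score test, and is higher with Fisher's test or at 0.025. The planned contrast adds a practical failure that is near certain at a 2% risk and still about an even chance at 10%. The consequence is for reporting and for the studies that follow. The change should be made, although it does not bear on patient protection in this trial.

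**What to change.** In 8.1.3, replace the one-sided six-cell contrast by the apixaban-minus-warfarin risk difference in ICH, stratified by the TIA, small-stroke and medium-stroke randomisation strata. Report it by day 30 and by day 180 with a two-sided 95% score-type interval that stays finite with empty cells; stratified Miettinen-Nurminen is one suitable choice.

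Reword 3.1 and 3.3 as estimation of this difference, in line with the pilot purpose in 8.1.5. Add a sentence that a non-significant result will not be read as absence of an increase. A margin is optional and for the sponsor to set in advance; an upper limit below it would support only the absence of an increase larger than that margin.

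The cost is wording in the protocol and analysis plan, with no change to scans or treatment. The downside is that the trial will probably be unable to claim no increase. With truly equal risks of 2/5/10/20%, the upper stratified limit falls below +5 points in only 25/18/13/10% of trials, and below +10 points in 78/57/40/27%. These two margins are illustrations, not proposals.

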**8.1.4 Potential Confounders**

Age and sex as well as a variety of clinical variables (e.g. CHADS2-VASc, CHA2DS2) that are risk factors for embolic stroke, and their associations with fatal or recurrent embolic stroke or hemorrhagic cerebral bleed will be examined. Other clinically relevant variables that are shown to differ between treatment regimens at enrollment will also be examined as potential confounders.

For missing data, both an intent-to-treat analysis (in which subjects are analyzed according to their randomized assignment) and a per-protocol analysis (in which subjects not treated according to their randomized assignment and/or with other major protocol violations are removed from this analysis) will be conducted. Sensitivity analyses to assess the effect of missing outcome data on the primary result will be conducted

**8.1.5 Sample Size and Power**

As a pilot, open-label study, this project is intended to generate data to be used in the development of future, larger studies. A total of 120 patients are expected to be available and eligible to participate in this study and up to 125 may be screened in order to yield 120 randomized participants.

Review of our database indicates the risk of fatal or recurrent stroke in patients with atrial fibrillation is approximately 20% with standard treatment . To calculate expected power in this study, this established risk was used as the basis for estimates that could be expected with this treatment if it is successful. Given the parameters of conducting a 2-sided test with alpha = .05, and equal allocation to treatment and control groups (50 patients per group), power calculations were conducted using various ratios of outcomes (i.e. fatal or recurrent stroke) in the control group compared to the experimental group. The following results were obtained:

Power	Detectable outcome Risk in control / Risk in experimental
80% power	2.30

90% power	2.52
99% power	3.00

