### **4.2.2 Total Number of Study Sites/Total Number of Subjects Projected**

The study will be conducted at University of South Florida (USF Health's South Center for Advanced Health Care, USF Health's Morsani Center for Advance Health Care , Tampa General Hospital), University of Louisville (hospital and clinic), University of California Los Angeles (hospital and clinic), and Bayfront Cardiovascular Sciences for a total of 4 enrolling sites.

Recruitment will stop when approximately 120 subjects meeting eligibility criteria are enrolled. To account for drop-outs as well as screen-failures up to 125 subjects will be consented and randomized.

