## 5.7 Subject Completion/Early Withdrawal

It will be documented whether or not each subject completed the clinical study. A subject is considered to have completed the study if he/she has taken all study medications for 6 months and has completed 6 month study assessments or withdrew from the study due to the occurrence of a recurrent embolic stroke, hemorrhagic transformation or death. If a subject does not complete the treatment phase, their data will be used for efficacy and for any safety analysis.

It is understood that withdrawals may occur during a trial. Each subject has the right to withdraw from the trial at any time for any reason without affecting the right to treatment by the investigator. Subjects who do not complete the treatment phase for other reasons then mentioned above, should be followed at day 14 and EOS visits, if possible. At minimum these patients should have a monthly phone call to assess AE/SAE and vital status if they are unable to continue follow-up in clinic.

Subjects needing to withdraw prior to the completion of the study and who do not agree to continue in follow-up should return to the clinic for completion of early withdrawal procedures, as outlined in table 1.

Reasons that a subject may discontinue the study include the following:

- Adverse events including recurrent stroke or hemorrhagic transformation
- Intercurrent illnesses
- Any significant new medical condition
- Protocol violation
- Non-compliance to study medication regimen

- Use of any investigational drug other than the study medication
- Intake of prohibited medication
- Pregnancy
- Subject withdrew consent or lost to follow-up
- Other (reason to be documented)

Withdrawals due to intercurrent illnesses or AEs will be fully documented in the CRF with the addition of supplementary information if available and/or appropriate. Withdrawals due to non-attendance will be followed-up by the investigator to obtain the reason for non-attendance.

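### 125 caps patients screened in 8.1.5 but patients randomized in 4.2.2; as a screening cap it yields 120 randomized only if at most 4% fail screening

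*Combined protocol and SAP*

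**What the plan says.** Four places bear on how many patients enter the trial.

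- **Section 8.1.5:** the plan counts on 120 eligible patients and sets the screening number in these words: "up to 125 may be screened in order to yield 120 randomized participants". Here 125 is counted before eligibility is settled.
- **Section 4.2.2:** "Recruitment will stop when approximately 120 subjects meeting eligibility criteria are enrolled". The next sentence reads: "To account for drop-outs as well as screen-failures up to 125 subjects will be consented and randomized". Here 125 is counted after eligibility is settled.
- **Section 8.1.6:** "For the 120 subjects to be randomized to either apixaban or warfarin, a random seed number was generated". Each of the three event types (TIA, small stroke, medium stroke) is allocated by "block randomization using four blocks of 10".
- **Section 8.1.5, power:** the calculation assumes "equal allocation to treatment and control groups (50 patients per group").

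Section 6.2 requires all inclusion and exclusion criteria to be confirmed before a patient is randomized. Section 5.7 says of non-completers: "If a subject does not complete the treatment phase, their data will be used for efficacy and for any safety analysis". Section 8.1.4 plans both an intent-to-treat and a per-protocol analysis. No screen-failure rate or dropout rate is stated anywhere.

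**The concern.** The same figure is attached to two different counts. A site or ethics board that follows 8.1.5 would close screening at 125 patients, however many had been randomized. One that follows 4.2.2 could randomize up to 125, with no limit on the number screened.

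Section 4.2.2 also fails on its own terms. Under 6.2 a screen failure is never randomized, so randomizing five more patients cannot make up for screen failures. The allocation list has no slots for those five patients either.

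The power statement then rests on a third number, 100, which is tied to neither 120 nor 125. A reader cannot tell what loss the trial expects or at which stage.

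**Working it through.** **1. The two definitions of 125.** In 8.1.5, 125 screened lead to 120 randomized, so all five extra patients are screen failures and none is a drop-out. In 4.2.2, 125 are randomized and the same five cover both kinds of loss. The allowance is 125 − 120 = 5 patients, and 5/125 = 4%.

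**2. Capacity of the list (8.1.6).** 3 event types × 4 blocks × 10 = 120 slots. Patients 121 to 125 have no allocation.

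**3. Yield of a screening cap.** Randomized = 125 × (1 − f), and screened needed for 120 = 120/(1 − f), rounded up, where f is the proportion failing screening. The documents give no value for f, so every row below is an assumption; the 4% row is the break-even point.

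| f (assumed) | Randomized from 125 screened | Screened needed for 120 |
|---|---|---|
| 4% | 120 | 125 |
| 10% | 112.5 (about 112) | 134 |
| 20% | 100 | 150 |
| 30% | 87.5 (about 87) | 172 |

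**4. The size used for power.** 2 × 50 = 100. This is 20/120 = 16.7% below 120 and 25/125 = 20% below 125. The plan explains neither step.

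**5. The plan's power table.** The formula is the normal approximation for two proportions with pooled null variance, two-sided 0.05:

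power = Φ{ [ |p₁ − p₂| − 1.96 √(2p̄(1 − p̄)/n) ] / √( (p₁(1 − p₁) + p₂(1 − p₂))/n ) }, with p̄ = (p₁ + p₂)/2 and n per arm.

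The tabled 80%, 90% and 99% at ratios 2.30, 2.52 and 3.00 come back only when 20% is the experimental risk. The control risks are then 46%, 50.4% and 60%, and n = 50 gives 79.9%, 90.1% and 99.0%. With n = 60 the same inputs give 86.7%, 94.6% and 99.7%, so the table was computed on 100 patients.

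**6. Power as the text describes it.** Section 8.1.5 assigns 20% to standard treatment. At a ratio of 2.30 the experimental risk is 20%/2.30 = 8.7%.

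- n = 60: Φ[(0.1130 − 0.1254)/0.0632] = Φ(−0.196) = 42%.
- n = 50: Φ[(0.1130 − 0.1374)/0.0692] = Φ(−0.352) = 36%.

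Going from 60 to 50 per arm costs about 6 points. The far larger drop from 80% comes from which arm carries the 20%, not from enrolment.

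**The case against.** The strongest reply is that no shortfall has been shown. A reader might infer that a cap of 125 will leave the trial below 120. The documents do not support that, because they give no screen-failure rate and the cap binds only above 4%. Nor does the count of 22 exclusion criteria in 4.3.2 establish a rate. Sections 4.1.1 and 5.1 draw laboratory results and the ECG from the hospital record where available. Section 6.1 reviews MRI results and schedules carotid imaging only if it was not done at admission. Much of eligibility may therefore be known before consent. This stands, with the limit that 8.1.5 speaks of patients screened and does not say that this means consented.

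A reader might also treat the 50 per group as a third, contradictory loss rate. It is not one. Calculating power on fewer patients than are randomized is conservative. More than 20% of 125 screened would have to fail before fewer than 100 were randomized. A set smaller than 60 per arm is also compatible with the per-protocol analysis in 8.1.4 and with the reference to adequate follow-up in 8.1.2. So 5.7 does not by itself rule out 50 per arm. This stands too.

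Finally, 8.1.5 is worded permissively, the stopping rule in 4.2.2 is already close to the right one, and the trial is a pilot. These points lessen the practical risk. They do not reconcile the two definitions, and they do not make extra randomizations a remedy for screen failures.

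**Conclusion.** The enrolment figures need correcting. Three findings rest on the text alone: 125 is defined in two incompatible ways, 4.2.2 uses randomizations to cover losses that occur before randomization, and the list described has 120 slots and cannot serve 125.

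The size of any shortfall is conditional. A screening cap of 125 gives 120 at up to 4% failure, and about 112, 100 or 87 at assumed rates of 10%, 20% or 30%.

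The 100 patients in the power calculation are an unexplained mismatch with 120, possibly an unstated loss allowance of about 17%.

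The low recomputed power (42% at 60 per arm, 36% at 50) should not be read as a consequence of the cap. It assumes a 20% control risk and a ratio of 2.30, and its distance from the tabled 80% is a separate error in the placement of the base rate.

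**What to change.** - **Section 8.1.5:** replace the limit on patients screened with a statement that screening continues until 120 are randomized.
- **Section 4.2.2:** remove screen failures from the reasons for the extra patients. Then either set the randomization ceiling at 120, which fits the existing list, or keep 125 and extend the list in 8.1.6 to match.
- **Dropout:** state one allowance and say which analysis set it applies to.
- **Power:** report it for all randomized patients under intent-to-treat (60 per arm), with a sensitivity line at 50 per arm labelled as the allowance (16.7% of 120). Use 20% as the control risk, as the text says. At a ratio of 2.30 the two lines read about 42% and 36%. The table's base rate has to be corrected at the same time, or the new lines will conflict with it.

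The cost is wording in two sections and a recomputed power line, plus a longer allocation list if 125 is kept. The downside is that more than 125 patients may be approached and consented. The target of 120 randomized does not change.

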### 1.2 Findings from pre-clinical and clinical studies

Currently, there are limited data regarding the early start of anticoagulation therapy following embolic stroke.

In the review of our local stroke database from October 2011 until December 2013, we examined the records of 336 small to medium stroke patients admitted to Tampa General Hospital with an ischemic stroke secondary to atrial fibrillation. The average age in our study population was  $75.3 \pm 1.83$  years of age. Stroke risk was similar to other AF groups in the literature, possessing an average CHADS2 score of  $2.6 \pm 0.26$  on admission; average CHA2DS2-VASc score was  $4.4 \pm 0.4$ . Average hospital stay was  $9.8 \pm 1.49$  days. We observed a  $24.7\% \pm 6.2\%$  mortality rate in our population prior to discharge. In addition, stroke survivors had a 5.1% recurrent non-fatal stroke risk. Patients with disabling or fatal

strokes were of a more advanced age than those who survived without severe disability ( $78.0 \pm 1.96$  years vs  $69.7 \pm 3.50$  years,  $p < 0.001$ ). Our data indicate that the risk of fatal to recurrent stroke is approximately 25 % with standard treatment (initiating anticoagulation approximately seven to fourteen days after signs and symptoms) for this group of patients.

The HAEST trial indicated that low molecular weight heparin results in a reduction in mortality and disability when used early (30 hours post stroke) in the treatment of ischemic stroke; however, this benefit is offset by an increased risk of intracranial hemorrhage

The previous studies on novel anticoagulation (NOAC) excluded subjects with a stroke/TIA within seven or less days; however, these randomized trials consistently demonstrated a lower risk of intracranial bleed compared to traditional anticoagulants ( see table 2).

[figure not shown]
ARISTOTLE followed a limited number of subjects (44) who suffered a stroke/TIA, between 7 and 14 days prior to randomization to treatment with either Apixaban or warfarin. There was only 1 subject in the warfarin group who suffered a major bleed. There were no recurrent stroke or systemic embolism in any of the 44 patients.

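### The power table in 8.1.5 does not follow from its stated inputs: at a 20% control risk and 50 per group, power is about 36%, 41% and 50%, not 80%, 90% and 99%

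*Combined protocol and SAP*

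**What the plan says.** Section 8.1.5 describes the study as a pilot meant to generate data for larger trials, then presents a power calculation. Its basis is "Review of our database indicates the risk of fatal or recurrent stroke in patients with atrial fibrillation is approximately 20% with standard treatment". The settings are "conducting a 2-sided test with alpha = .05" and "equal allocation to treatment and control groups (50 patients per group". The table gives detectable ratios of control risk to experimental risk of 2.30 (80% power), 2.52 (90%) and 3.00 (99%).

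Other parts of the document bear on those inputs:

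- **Rate.** Section 1.2, on the local stroke database, says "the risk of fatal to recurrent stroke is approximately 25 % with standard treatment". The components given there are 24.7% ± 6.2% mortality before discharge, with no cause stated, and "stroke survivors had a 5.1% recurrent non-fatal stroke risk".
- **Source.** Section 8.1.5 attaches reference 9 to the 20%. In the reference list that is a published apixaban trial. The report on the local database is reference 12.
- **Population.** The database cohort is 336 admitted patients with small to medium stroke. The trial also enrols TIA. Section 5.2 intends equal numbers in the three types, and 8.1.6 says "Each subgroup of stroke type (small stroke, medium stroke and TIA) was randomized" in four blocks of 10, so 40 of the 120 places are for TIA.
- **Outcome.** The power calculation uses fatal or recurrent stroke. Sections 3.2 and 8.1.2 use fatal stroke, recurrent ischemic stroke or TIA. Section 7.1 lists new hemorrhagic stroke in place of TIA.
- **Size.** Section 8.1.5 plans 120 randomised out of up to 125 screened, yet computes power on 50 per group. Section 4.2.2 says "up to 125 subjects will be consented and randomized".

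**The concern.** A halving of risk from 20%, tested with 50 patients per group, is not something a trial detects with 80% power, so the table looks wrong on sight. The 99% row is plainer still: with 50 per group and a 20% control risk, no treatment effect can reach 99%.

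Section 8.1.2 tests the overall treatment effect at P<0.05. A reader told that a ratio of 2.30 would be found four times in five may take a non-significant result as evidence against an effect of that size. If true power is nearer two in five, that reading is wrong. The table could also mislead those who plan the larger study that this pilot is meant to inform.

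**Working it through.** **Inputs (8.1.5).** Control risk p_C = 0.20; n = 50 per group; two-sided alpha 0.05, so z = 1.96; ratio R = p_C/p_E of 2.30, 2.52 or 3.00. The planned 120 randomised gives n = 60.

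**Formula (pooled-variance comparison of two proportions).** Let d = p_C − p_E and p̄ = (p_C + p_E)/2. Then s0 = √(2p̄(1−p̄)/n), s1 = √(p_C(1−p_C)/n + p_E(1−p_E)/n), and power = Φ((d − 1.96·s0)/s1).

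**Step 1. The table as labelled, with 20% in the control arm.**

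| R | p_E | d | s0 (n=50) | s1 (n=50) | Power, n=50 | Power, n=60 | Stated |
|---|---|---|---|---|---|---|---|
| 2.30 | 0.087 | 0.113 | 0.0701 | 0.0692 | 36% | 42% | 80% |
| 2.52 | 0.079 | 0.121 | 0.0693 | 0.0683 | 41% | 48% | 90% |
| 3.00 | 0.067 | 0.133 | 0.0680 | 0.0667 | 50% | 58% | 99% |

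First row: (0.113 − 1.96 × 0.0701)/0.0692 = −0.35, and Φ(−0.35) = 0.36.

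**Step 2. Could another method explain the table?** With n = 50 and 20% in the control arm, the three rows give:

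- one-sided test: 49/54/63%
- unpooled variance: 37/42/52%
- log risk ratio: 34/38/45%
- log odds ratio: 35/39/47%
- arcsine: 38/43/53%
- Fisher's exact: 26/30/38%

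None comes close. If the experimental arm has no events at all, d = 0.20, s0 = 0.0600, s1 = 0.0566 and power is 93%, so 99% is out of reach. For 80% power with 50 per arm, the ratio would have to be about 8.0 (20% versus 2.5%). At ratio 2.30, 80% power needs about 150 per arm.

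**Step 3. Reversed roles.** Put 20% in the experimental arm and 0.20 × R in the control arm, with n = 50:

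| R | p_C | p_E | Power | Stated |
|---|---|---|---|---|
| 2.30 | 0.460 | 0.20 | 79.9% | 80% |
| 2.52 | 0.504 | 0.20 | 90.1% | 90% |
| 3.00 | 0.600 | 0.20 | 99.0% | 99% |

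All three rows match.

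**Step 4. Other control risks, 60 per arm, ratio 2.30.** Half-width of the 95% interval for the risk difference = 1.96·s1.

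| p_C | p_E | Power | Half-width (points) |
|---|---|---|---|
| 5% | 2.2% | 13% | 6.6 |
| 10% | 4.3% | 22% | 9.2 |
| 20% | 8.7% | 42% | 12.4 |
| 25% | 10.9% | 52% | 13.5 |
| 28.5% | 12.4% | 59% | 14.1 |
| 30% | 13.0% | 62% | 14.4 |

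The 28.5% is a constructed figure: 0.247 + (1 − 0.247) × 0.051 = 0.285. It adds deaths of unstated cause to non-fatal recurrences, a sum the protocol does not itself make. About 87% of it (0.247/0.285) is pre-discharge death. At the lowest risks only a few events are expected per arm, so those rows are approximate.

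**The case against.** **Pilot status.** The trial is declared a pilot, and 8.1.2 already plans a 95% interval for the difference between arms. That lessens the consequence, because a pilot needs no 80% power. It does not make the printed figures correct.

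**The two rates are compatible.** Both are labelled approximate, and 24.7% ± 6.2% runs from 18.5% to 30.9%, which covers both. So the difference is a matter for reconciliation, not proof that 20% is wrong.

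**The size figures.** Using 50 per group instead of 60 lowers power, so it is not the source of the inflated table. It may be an unstated allowance for drop-out. The 125 screened versus 125 randomised may be a slip of wording.

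**A stronger reading that fails.** A reader might infer that the event rate is overstated and that this is why the power is overstated. The documents do not support it. The table fails with the 20% accepted in full. The competing local figures, 25% and the constructed 28.5%, are higher and would raise power (45% and 51% at ratio 2.30 with 50 per arm, against 36%). The remaining mismatches pull both ways. A TIA stratum, or removing non-stroke deaths, may lower the rate; counting TIA as an outcome and following patients to 180 days may raise it.

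Nor do the patients in 1.2 of whom it is said "There were no recurrent stroke or systemic embolism in any of the 44 patients" supply a control rate. They entered 7 to 14 days after their event, they pool apixaban and warfarin, and no follow-up time is given.

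**Conclusion.** The power table is wrong as written. On its own stated inputs, power is about 36%, 41% and 50%, and with the planned 60 per arm about 42%, 48% and 58%. This rests on a two-sided 0.05 comparison of two proportions without loss to follow-up; the other standard methods tried do not rescue it. At 60 per arm and ratio 2.30, power stays at or below 62% for every control risk from 5% to 30%.

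Reversal of the two risks is the likely cause, since it reproduces every row. It remains an inference, because the plan does not show its calculation. The control risks it implies, 46% to 60%, are well above anything reported in 1.2.

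The weak basis for the 20% is a real but secondary fault: two figures for the same local data, a citation to a different study, a described cohort without TIA patients, and an outcome that matches neither composite. Its net effect on the event rate has no determinable sign.

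**What to change.** 1. In 8.1.5, delete the 80%, 90% and 99% claims. Recompute with the assumed risk in the control arm, 60 per arm, over control risks of 5% to 30% including 20% and 25%. Step 4 of the working gives the values for ratio 2.30.
2. State the expected 95% half-width for the risk difference, about ±12 points at 20% versus 8.7%, as the main description of what the pilot can show.
3. Reconcile the 20% in 8.1.5 with the 25% in 1.2, cite the source actually used, and say how TIA patients enter the assumed rate.
4. Use one composite definition in 3.2, 7.1, 8.1.2 and 8.1.5, and assume a rate for that composite.
5. Use one number randomised in 4.2.2 and 8.1.5, and either explain the 50 per group or replace it.

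The cost is a less favourable power statement. No extra patients, visits or data are needed.
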